6.2 Exclusion Criteria

Patients are to be excluded from the trial if any of the following criteria is fulfilled:

- 1) on-going immunomodulatory treatment
- 2) pregnancy or breast-feeding
- 3) weight below 40 kg
- 4) clinically relevant on-going infection
- 5) chronic infections
- 6) positive screening test for hepatitis B, C HIV or tuberculosis
- 7) any change of psychotropic medication within the previous 4 weeks
- 8) “much” or “very much improved” already at baseline according to CGI-I i.e. scores of 1 or 2 by the clinician
- 9) severe heart failure (NYHA grade IV) or other severe heart disease or history of cardiac arrhythmia or myocardial infarction
- 10) unable to make an informed decision to consent to the trial
- 11) in compulsory treatment
- 12) treatment with clozapine within the last 2 months
- 13) previous treatments with immunosuppressive agents
- 14) malignancy currently or within 2 years prior to inclusion

6.3 Withdrawal of patients

The patients can at any time choose to stop participating in the study without giving any reason for this. If possible, the reason for the patient leaving the study should be recorded. Data collected up to the subject's leaving the study will be used in the analysis of the study.

The investigator can remove a patient from the study due to safety reasons or in case the patient is not able to comply with the protocol.

7 STUDY PLAN AND DESIGN

7.1 Study outline

After a screening visit, patients who meet the inclusion criteria will be asked to participate in this study. Plasma drug levels of the on-going medication will be measured before inclusion. Patients will be allocated to treatment with rituximab. If the patient is treated with anti-hypertensive drugs these shall be withdrawn 12 hours prior to rituximab treatment. Patients will receive the premedication 1-2 h prior to rituximab in their home or at the clinic. A nurse, experienced with rituximab treatment, will accompany the patient during the hours of rituximab infusion. Blood pressure will be measured before and after treatment and at every change of the speed of the infusion. The temperature will be measured before and after treatment. Mabthera will be administered according to the guidelines for safety of the patients, see supplementary file "*Rutiner för behandling med Mabthera inom ramen för studierna RITS-PO och RITS-PS*". Patients will rest for an hour after the termination of the infusion and will not be left alone during this time.

All patients will be treated with the study drug rituximab on one single occasion and followed for a total of 1 year. They will have a total of 13 visits (screening prior to inclusion can be divided into more than one visit if necessary) with a clinician or research nurse who is experienced with rituximab and with psychiatric patients. An extensive psychiatric interview will be performed with each patient and his/her next of kin at baseline. We will also review medical records in order to document previous symptomatology and treatment trials. A short video recording is optional. All participants will be examined for psychiatric, neurological and motor symptoms, cognitive functioning, and a range of biomarkers. However only blood sampling and the interview are prerequisites for participation, all other examinations and tests are optional. Prior and post treatment the optional lumbar puncture and fMRI will be performed for further diagnostic evaluation and assessment of blood-brain barrier function. Faeces samples will also be collected prior to treatment and endpoint 1 of this study (optional) as well as gut biopsy prior to treatment (optional). Patients are requested to remain on their standard psychiatric treatment until endpoint 1, and treatment should be stable for the last 1 month prior to baseline. Patients are allowed adaption of their on-going psychiatric treatments after week 20 but also earlier if the treating physician deems this necessary.

Biological and psychiatric assessments will be performed at pre-decided time points (see table 1). Patients will be followed by additional visits to a nurse for in-between visits.

Side effects will be monitored at each visit. Patients will continue their regular visits with the psychiatric staff.

At endpoint 1 (20 weeks) a separate interview lasting approximately 45 minutes will be held for a qualitative analysis.

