7.1.1 Data collection, management, and analysis

Demographic background data and treatment history will be collected from interview and medical records at baseline.

Assessments will be made with established and well-validated rating scales and questionnaires in addition to one research interview that was developed by the principal investigator (PNISSI) (see list of all rating scales and questionnaires below). Sampling of biological materials will be done by a standard operating procedure (SOP) used for sampling for other current cohorts. We will also perform laboratory tests in a highly structured manner with well-validated methods in collaboration with researchers at Örebro University and Karolinska Institutet. Samples will be frozen and stored in Region Örebro County biobank (458) at -80 °C until analysis. All data collection forms will be stored at a safe place within Örebro hospital, Region Örebro County.

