7.1.3 Biochemical and other measures

There is still insufficient knowledge concerning inflammatory/immunological mechanisms of psychiatric disorders. Therefore, in order to increase our understanding and to extend the interpretational potential of clinical findings from our exploratory study, we will assess relevant immunological parameters, autoimmune biomarkers, genetic SNPs, etcetera. Additionally, we will apply routine safety biochemistry, recommended for rituximab in clinical use.

Also all subjects will be asked if they have received standard vaccinations and if they have had chicken pox, i.e. immunity to Varicella zoster (positive antibodies if unknown). If not then vaccinations must precede the treatment with rituximab.

Tests in blood and cerebrospinal fluid (CSF)

Blood and CSF will be drawn at baseline (before intervention), and at week 20 (after intervention). Analyses will include:

Blood only

At baseline, week 20 and week 40:

- Routine clinical tests for basic haematology, 5-partsdiff including neutrophil and lymphocyte count to be able to make the neutrophil/lymphocyte ratio and platelet counts, glucose, infection, liver function, renal function, electrolyte balance, thyroid status, 25-OH-vitamin D, PTH, vitamin B12, folat
- Expression levels of selected pro-inflammatory genes (e.g. IL-1 β , caspase, IL-6, IL-8), analysed using real-time PCR and DNA microarray technology

At baseline and week 20:

- Biomarkers for gut permeability (e.g. I-FABP, GLP-2)

At baseline, week 5, 12, 20, and 40:

- B-cell populations monitoring, by flow cytometric phenotyping (e.g. CD19, CD24, CD27, CD38, CD5), to quantify the impact of rituximab treatment (*if not normalized in week 40 a repeated test will be made in week 52*)

Routine clinical tests for 5-partsdiff including neutrophil and lymphocyte count to be able to make the neutrophil/lymphocyte ratio and platelet counts. *Only at prescreening/baseline:*

- Serology for hepatitis B, C and HIV
- QuantiFERON test (interferon- γ release assay) to check for response to *Mycobacterium tuberculosis*
- Drug concentration of psychotropic medication
- Assessment of autoimmune reactions against cerebral antigens (whole blood sample, stored in – 80° C) (application of novel findings from our group)

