- Illicit drug screen (baseline and week 20)

At baseline and week 20:

- 30 ml of urine, early morning sample, for assessment inflammatory markers, similar to those in blood

Brain

At baseline and week 20:

- fMRI for assessment of altered activity and extra cellular water, which may be a sign of inflammation

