8.2 Administration of study drugs

A MabThera dose of 1000 mg will be given as intra-venous infusion in 1000 ml physiological saline (0.9 %, any brand provided by the pharmacy). Before administration of MabThera all patients will be given pre-medication to prevent or reduce possible side effects from MabThera.

Premedication is delivered 1-2 hours prior to rituximab and consists of T. Paracetamol 1000 mg, T. Loratadine 10 mg and T. Betapred (Betamethasone) 0.5 mg x 12 p.o (dissolved in a glass of water) in order to reduce the incidence of infusion-related reactions.

Patients remain on their stabilized treatments with psychotropic drugs during the first phase (20 weeks) of the study.

MabThera will be administered on one single occasion.

The MabThera treatment is administrated at the Rheumatology clinic at Örebro University Hospital. Study staff at the department of Rheumatology will prepare the saline bag for each patient infusion, adding MabThera. All bags will be labelled with a study specific label (**Error! Reference source not found.**). Each bag for infusion will be prepared just in time for each visit.

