The side effects of rituximab include infusion reactions, severe skin and mouth reactions, hepatitis B virus reactivation and in extremely rare cases (1/25000 in patients with rheumatoid arthritis (102), progressive multifocal leukoencephalopathy (PML), a serious brain infection caused by the JC virus. We will collaborate with a senior rheumatologist who is experienced with rituximab. Since the treatment may activate latent infections, all patients will be screened for hepatitis and HIV prior to the study. The patients will be pre-medicated to reduce the risk of infusion-related side effects, and they are carefully monitored during the course of the study.

The reason to not use a standard drug for inflammation, such as cortisone, is because it may induce mania in susceptible individuals and is therefore not suitable for psychiatric patients.

We will film the patients on three different occasions. This is because we want to be able to show the patient if there is a treatment effect or not. It may also enable a completely external assessment of treatment effects. Since rituximab has not been tested in trials of psychiatric disorder an effect of the drug can be questioned. In such case we possibly could show video clips of treatment effects, if the patient allows it (but this is not included in this study). The film clips may also support a request for further treatment with the drug.

Early onset of severe psychiatric disability is associated with a particularly poor long-term prognosis. This is often the case for schizophrenia. Delayed treatment may cause persistent brain damage if associated with inflammation in the brain (which is presumed). We believe that earlier treatments may have better effects on the symptoms than treatment that are first provided after many years with the disease. Also, rituximab is frequently used for treating children and adolescents with MS (103). Thus it would be unjust to exclude them from participation in a trial with a medication that may prove helpful.

The patients will remain on their standard psychiatric treatment throughout the course of the study and are allowed to adapt their medication dose accordingly. Therefore, we do not put the patient's mental health at risk. The side effects of rituximab do not coincide with those that can be expected from psychiatric medication (apart from possibly clozapine), which implies low risk for add-on side effects.

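### Sections 7.1, 8.2 and 12.3 word the rule on psychotropic changes before week 20 differently, and a response after such a change counts as a response without being shown

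*Combined protocol and SAP*

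**What the plan says.** Three places in the combined protocol and SAP deal with psychotropic treatment before the week-20 endpoint.

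- Section 7.1 makes a request, "Patients are requested to remain on their standard psychiatric treatment until endpoint 1", followed by an exception: "Patients are allowed adaption of their on-going psychiatric treatments after week 20 but also earlier if the treating physician deems this necessary".
- Section 8.2 is unqualified: "Patients remain on their stabilized treatments with psychotropic drugs during the first phase (20 weeks) of the study".
- Section 12.3, in the risk/benefit discussion, says: "The patients will remain on their standard psychiatric treatment throughout the course of the study and are allowed to adapt their medication dose accordingly".

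Stability before entry is enforced. Section 6.2 excludes patients with "any change of psychotropic medication within the previous 4 weeks".

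Response is defined by scores alone: a 40% PANSS reduction (section 10.1), or a mean CGI-I below 2.5 across clinician, patient and next of kin (section 10.2.1). The clinical analysis set is a modified intention-to-treat set of everyone dosed, with a completer analysis added. Section 10.1 states the aim of going on to a controlled study if two or more patients improve significantly, a term it does not define. Section 10.2.2 compares biomarkers between responders and non-responders.

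On recording, section 7.1.1 says: "Demographic background data and treatment history will be collected from interview and medical records at baseline". Section 7.1.3 lists "Drug concentration of psychotropic medication" among tests done only at prescreening or baseline, whereas the illicit drug screen is repeated at week 20.

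**The concern.** With no control arm, nothing nets out a change in co-treatment. A patient whose psychotropic is started or increased before week 20, and who then meets a response threshold, is counted in the same way as a patient on unchanged background treatment. The reader of the results cannot tell the two apart.

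Three results could be affected. The first is the proportion of responders. The second is the set of biomarker comparisons, where such a patient sits in the responder group. The third is the two-patient aim, if significant improvement there means response; one such patient would then be half of the number needed. The sponsor regards stability before baseline as important enough to be an exclusion criterion, but the analysis section does not carry that through to the treatment period.

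**Working it through.** **Step 1: the three wordings side by side.**

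| Section | Stability to week 20 | Change before week 20 |
|---|---|---|
| 7.1 | requested | allowed on the physician's judgement |
| 8.2 | stated as fact | no exception given |
| 12.3 | standard treatment kept for the whole study | dose adaptation allowed; no week-20 boundary, no stated condition |

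Sections 7.1 and 8.2 can be read together as a default and its exception. Section 12.3 drops both the boundary and the condition.

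**Step 2: what section 10 does with such a patient.** Every dosed patient is in the analysis set. A mean CGI-I below 2.5 is response and 2.5 or higher is non-response; PANSS response depends on the percentage reduction only. A scored patient is therefore always classified, and a medication change plays no part. The open wording on possible confounders (sections 10.2.2 and 10.2.3) belongs to models of continuous scores and cannot alter a responder count. Sections 10.1 to 10.2.4 contain no table, listing or sensitivity analysis by medication change.

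**Step 3: how much it could matter.** The plan gives no error rate for the two-patient aim and no rate of medication change. Its one derived figure, 0.64 CGI-I points, is reproduced by t(0.975, 11 df) × 1/√12 = 0.635, but has no bearing here. The following are therefore assumptions:

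- q = share of patients with a sustained new or increased regular psychotropic before week 20
- h = share of those who then meet the response definition
- no effect of rituximab

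With n = 12, P(at least 1) = 1 − (1−p)^12 and P(at least 2) = 1 − (1−p)^12 − 12p(1−p)^11.

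*Post-change responses alone, p = q × h:*

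| q | h | p | P(at least 1) | P(at least 2) |
|---|---|---|---|---|
| 10% | 10% | 0.01 | 11.4% | 0.6% |
| 20% | 10% | 0.02 | 21.5% | 2.3% |
| 30% | 10% | 0.03 | 30.6% | 4.9% |
| 20% | 20% | 0.04 | 38.7% | 8.1% |
| 30% | 20% | 0.06 | 52.4% | 16.0% |

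For example, at p = 0.03: 1 − 0.69384 − 0.25751 = 0.04865. A 5% chance of reaching 2 of 12 needs q × h of about 3% (p = 0.0305).

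*With background response.* Section 12.4 accepts that symptoms fluctuate and may remit spontaneously. Assume b = 5% respond for other reasons, so p = b + (1−b) × q × h, with h = 10%:

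| q | p | P(at least 2) |
|---|---|---|
| 0 | 0.0500 | 11.8% |
| 10% | 0.0595 | 15.7% |
| 20% | 0.0690 | 19.9% |
| 30% | 0.0785 | 24.2% |

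**Step 4: the price of a stricter count.** Suppose patients with such a change are recounted as non-responders, changes are independent of response, and the true response rate is r. Then p = r × (1−q), and P(at least 2 of 12) is:

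| r | q = 0 | q = 10% | q = 20% | q = 30% |
|---|---|---|---|---|
| 15% | 55.7% | 49.6% | 43.1% | 36.4% |
| 25% | 84.2% | 79.0% | 72.5% | 64.8% |
| 35% | 95.8% | 93.0% | 89.0% | 83.2% |

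**The case against.** The strongest reply has four parts.

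**The wording conflict is mild.** In section 12.3, the phrase about the whole study governs staying on standard treatment, not adapting the dose. The sentence can be read as a short form of section 7.1, which allows adaptation after week 20 and, on medical judgement, before it. This largely stands. A reader might infer a flat three-way contradiction, and the documents do not support that. What remains is that section 8.2 omits the exception and section 12.3 omits the condition, so the texts still need to be aligned.

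**Counting is not undefined.** A reader might infer that the plan leaves post-change responses unclassified. It does not: applied as written, the score-only rules count all of them. This stands, and it moves the point from counting to display.

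**Recording may already happen.** A reader might infer that changes go unrecorded. The CRF and the source data list (section 13.2) are not in the documents. Table 2 has nurse progress notes, regular psychiatric visits continue, and the optional MRI session asks about recent benzodiazepines and hypnotics. The schedule has a gap, but that is not proof of missing data.

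**The effect is assumed and may be small, and the recount may cost more than it saves.** Entry requires treatment resistance, so h may be low. At h = 10%, post-change responses alone stay below 5% for every q shown. With background response they add 4 to 12 percentage points, while at r = 25% the recount loses 5 to 19. More extreme inputs give far larger figures: with a third of patients changing, 40% of them responding and 5% responding among the rest, P(at least 2) is 61.9%. Nothing in the documents supports such inputs. This is a good reason not to make the recount the main analysis. It is not a reason against showing it, since the supportive count replaces nothing.

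The primary outcome is change in PANSS score, and the two-patient line is an aim in a pilot without a power calculation. Both facts limit the harm.

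**Conclusion.** The point holds as a matter of consistency and display. The three sections word the rule differently and must be reconciled; no view is taken here on which clinical rule is right. As written, every response counts, including one after a new or increased psychotropic, and no planned analysis makes such responses visible. In an uncontrolled study of 12 this can affect the responder count, the biomarker comparisons and, if significant improvement means response, the two-patient aim.

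The size is unknown. The figures rest on assumed values of q, h and b and show only what follows from them; the effect is larger only if changes are both common and followed by response. The next step would be a controlled study, which limits the consequence of a mistaken decision to continue. Severity is minor to moderate.

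**What to change.** 1. Reconcile sections 7.1, 8.2 and 12.3 so that they state one rule. Its content is for the sponsor.
2. If the CRF does not already do so, record each psychotropic change up to week 20 with drug, dose and date. The dates also show whether an improvement seen at week 12 came before the change.
3. Keep the all-treated analysis as the main one. Beside it, report a 2×2 count of change (yes/no) by response (yes/no), for PANSS and for CGI-I. This is a group-level display, as section 16 requires, although with 12 patients some cells may be very small.
4. Pre-specify one supportive count in which responders with a sustained new or increased regular psychotropic before week 20 are treated as non-responders. As-needed doses are left out. Fix a single definition of sustained before the data are seen. Report the number of responders and the two-patient result both ways.

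The cost is a little extra recording, if it is not already in place, one small table per response definition and one extra count. The supportive count can also class a true responder as a non-responder: at an assumed 25% response rate, P(at least 2 of 12) falls from 84% to 79, 73 or 65% if 10, 20 or 30% of patients change. It must therefore not replace the main count.

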12		
 • Assessments (PANSS, CGI-I**, PGE, CGI-S) • Side-effects, AAR • Patient evaluated improvement (PGE) • Blood sample (B-cell population) • Video recording II
16 (+/- 1 week)	Nurse check-up	
 • Side-effects, AAR • Patient evaluated improvement (PGE)
20-23	20 w	
Interview + Assessments (PANSS, CGI-I*, PGE, CGI-S, and MINI, psychiatric rating scales, GAF, EQ-5D, Level 1 Cross-cutting symptom measure of global symptom severity)
 
 • PSP • Side-effects, AAR

		
• UKU• Client satisfaction questionnaire (CSQ)• Physical examination• Cognitive and motor tests (from PNISSI and Nine-Hole Peg Test)• Video recording III• Blood sample• Lumbar puncture (optional)• Faeces sample (optional)• Urine sample• fMRI (optional)
20-24	Clinician	
• Extended interview for content analysis
24 (+/- 1 week)	Nurse check-up	
• Patient evaluated improvement (PGE)• Side-effects, AAR
32 (+/- 1 week)	Nurse check-up	
• Patient evaluated improvement (PGE)• Side-effects, AAR
40-43	40 w	
• Interview + Assessments (PANSS; CGI-I*, PGE, CGI-S, and MINI, psychiatric rating scales, GAF, EQ-5D)• PSP and BBQ• Client satisfaction questionnaire (CSQ)• Side-effects, AAR, UKU• Blood sample• Cognitive tests• Video recording IV
52 (+/- 1 week)	1 year follow-up	
• Assessments (PANSS, CGI-I, PGE, CGI-S, GAF)• Side-effects, AAR

*if the patient is treated with antihypertensive medication these should be withdrawn 12 h prior to the rituximab treatment

**evaluated by clinician and next-of-kin

Table 2

Week			-4 - 0	0	1	2	5	8	12	16	20	24	32	40	52
Visit			1	2	3	4 (nur se)	5	6 (nur se)	7	8 (nur se)	9	10 (nurse /other)	11 (nur se)	12	13
Activity/ Assessment number	CRF Y/N	Time to complete		Pre-Study Screening	Baseline 1:0						20w			40w	
ENROLMENT Eligibility screen, Consent form, Demographics questionnaire, Treatment history, PNISSI, Physical examination, FTF-Brief. Routine blood tests, hepatitis, HIV, TB. Vaccination check up (+varicella). Therapeutic drug monitoring, U-illicit drug screening,		60 min	x												
Pregnancy test (females)			x												
INTERVENTION Rituximab, Dose 1: 4.5h				x:1											
ASSESSMENTS MINI, Psychiatric rating scales		45 min	x								x		x	x	x

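### Psychotropic medication may change at any time before the endpoint-1 PANSS, the sections on this disagree, and the analysis has no rule for scores rated after a change

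*Combined protocol and SAP*

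**What the plan says.** Three sections of the protocol speak to concomitant psychotropic treatment, and Table 1 sets the timing of the rating.

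- Section 7.1 (Study outline): "Patients are requested to remain on their standard psychiatric treatment until endpoint 1". The next sentence begins "Patients are allowed adaption of their on-going psychiatric treatments after week 20" and extends this to earlier changes that the treating physician considers necessary. The section also ties the visit to a week: "At endpoint 1 (20 weeks) a separate interview".
- Section 8.2 (Administration of study drugs): "Patients remain on their stabilized treatments with psychotropic drugs during the first phase (20 weeks) of the study".
- Section 12.3 (Risk/benefit assessment) keeps patients on standard treatment for the whole study and allows them to adapt the dose. It sets no time limit.
- Table 1 (Study plan), row for weeks 20-23, labelled 20 w: "Interview + Assessments (PANSS, CGI-I*, PGE, CGI-S, and MINI, psychiatric rating scales, GAF". The same row holds PSP and the blood sample.

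At entry the plan treats a recent change as disqualifying. Section 6.2 excludes patients with "any change of psychotropic medication within the previous 4 weeks".

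The primary outcome is the change in PANSS from baseline (synopsis; sections 5.2 and 10.2.1). Section 10.2.1 defines a modified intention-to-treat set and a completer analysis. It does not mention scores obtained after a change in psychotropic medication.

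**The concern.** In an open single-arm study, the change from baseline is the whole of the evidence. Anything else that changes between baseline and the endpoint-1 rating enters that difference, and no comparison group balances it. A psychotropic change is the most obvious candidate. The plan guards against it at entry but has no matching protection at the endpoint, either in conduct or in analysis.

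A change made on the treating physician's judgement before the visit is within the protocol, so a deviation listing would not necessarily show it. The affected results would be the PANSS change, the count reaching the 40% cut in section 10.1, the CGI-I, CGI-S and PSP results at endpoint 1, and the differences in blood markers between baseline and week 20.

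**Working it through.** The plan gives no figure on this point, so there is none to reproduce. The check compares the text and adds a little arithmetic.

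**1. What each statement allows before the endpoint-1 PANSS**

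| Source | Weeks 0 to 20 | After week 20, before the rating |
|---|---|---|
| 7.1, stability request | Patients are asked not to change | Asked not to change if endpoint 1 means the visit; silent if it means calendar week 20 |
| 7.1, adaptation sentence | Allowed on the physician's judgement | Allowed outright if week 20 is a date; on the physician's judgement if it names the visit |
| 8.2 | Treatment described as stable | Outside the stable phase if 20 weeks is a calendar count |
| 12.3 | Dose adaptation allowed | Dose adaptation allowed |

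The rows do not agree in either column. On every reading of week 20, at least one statement permits a change before the rating.

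**2. Length of the exposure**

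The part after week 20 is 23 − 20 = 3 weeks. This is shorter than the 4 weeks that section 6.2 treats as too recent at entry. The full period in which a permitted change can precede the rating is week 0 to week 23. Closing the late window alone would remove at most 3 of those 23 weeks.

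**3. Handling in the analysis**

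The modified intention-to-treat set keeps everyone who received rituximab, and the completer set keeps everyone who finished. Neither separates patients whose medication changed. The missing-data text in section 7.1.2 concerns unanswered items within a scale. Psychotropic drug concentrations are scheduled only at prescreening/baseline (section 7.1.3), and the row for weeks 20-23 lists no medication review.

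**4. Size**

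Let M be the effect of a medication change on one patient's endpoint PANSS, with either sign. If k of 12 patients are affected by the same M, the mean change shifts by k × M / 12. The documents give neither k nor M. As an assumption, take M between 10 and 20 points:

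- k = 1: 10/12 = 0.83 to 20/12 = 1.67 points
- k = 3: 30/12 = 2.5 to 60/12 = 5.0 points

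One patient moved across the 40% cut changes the proportion of responders by 1/12 = 8.3 percentage points.

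**5. What a sensitivity analysis can use**

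Up to endpoint 1, Table 1 schedules PANSS at weeks 0, 12 and 20-23. For a change after week 12, the last earlier scheduled score is from week 12, which is 20 − 12 = 8 to 23 − 12 = 11 weeks before the endpoint-1 rating. For a change between baseline and week 12, the last earlier score is the baseline itself, so the substituted change is zero.

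**The case against.** The strongest reply is that week 20 is the name of a visit, not a date. Table 1 labels the row for weeks 20-23 as 20 w, section 7.1 equates endpoint 1 with 20 weeks, and section 10.2.3 speaks of week 20 scores. Read that way, adaptation after week 20 means adaptation after the endpoint-1 visit, and the two sentences in 7.1 largely agree. This is a fair reading, and it weakens any claim that the 20-23 window is by itself the fault. It does not remove the problem, because the same sentence permits earlier changes and section 12.3 sets no time limit.

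A reader might infer several stronger things that the documents do not support:

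- **That the problem is confined to weeks 20-23.** Changes are permitted from week 0, so aligning the window with the stability period would leave most of the exposure in place.
- **That the bias favours rituximab.** A change may follow worsening, and its effect could go either way.
- **That one such patient supplies half of the two improvers needed to continue.** Section 10.1 does not define significant improvement and does not tie it to the 40% cut.
- **That a medication change would readily carry a patient across the 40% cut.** Section 6.1 requires failure of at least two drug treatments, each tried for at least 4 months. Nothing in the plan shows that a short adjustment would produce so large a response.
- **That changes will go unrecorded.** The CRF is not among the documents. It can only be said that the protocol text does not require the dates and does not use them.

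**Conclusion.** The point stands as an inconsistency in the medication statements combined with a gap in the analysis plan. Psychotropic treatment may be changed, within the protocol, at any time from week 0 up to an endpoint-1 rating made as late as week 23. The analysis would count the resulting score as a rituximab effect.

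The direction is unknown and the size cannot be derived from the documents. The shift of 0.8 to 1.7 points in the mean rests on an assumed 10 to 20 point effect in one of 12 patients, and it grows in proportion to the number affected. The conclusion about timing does not depend on that assumption or on how week 20 is read. It should be addressed because the remedy is cheap and the design has no control arm to absorb the effect.

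**What to change.** 1. Reconcile sections 7.1, 8.2 and 12.3 with one another and with the week 20-23 window in Table 1. Which medication rule applies is for the sponsor to decide.
2. Require the date of every psychotropic change, and the dates of each endpoint-1 rating and blood sample, to be recorded so that their order is known for every patient.
3. Report how many of the 12 patients had a change before the endpoint-1 rating.
4. Add to section 10.2.1 a pre-specified sensitivity analysis of the PANSS change and the responder count. For patients with a prior change, it would use the last PANSS before the change or count them as non-responders.

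The cost is short text edits and a few date fields, with no extra visit. The limitation should be stated: after week 12 the substitute is the week-12 score, and before week 12 it is the baseline. The analysis then answers a somewhat different question, so it should stand beside the primary analysis and not replace it.
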